### **9.3. Populations for Analyses**

The analysis populations will consist of participants as defined below:

- The ITT population includes all randomized participants. Participants will be summarized according to the randomized study intervention.
- The safety population includes all treated participants who receive  $\geq 1$  administration of study intervention. Participants will be summarized according to the study intervention they actually receive.

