## 4. Study Design

### 4.1. Overall Design

This is a prospective, randomized, controlled, parallel-group, open-label, single-center study in participants with DED.

This study consists of 2 visits: Screening and the Application Visit (Day 0). A study schema is located in Section 1.2 and the Schedule of Visits and Procedures is located in Section 1.3.

Participants will be randomized (in a 2:1 ratio) at Screening to either intranasal or extranasal acute (single) application of the ITN, which they will apply accordingly for approximately 3 minutes during the Application Visit. Approximately 36 participants with DED will be enrolled at a single site in the United States.

At Screening, and prior to any testing, participants will be provided with an IRB-approved ICF which they will have the opportunity to review and ask questions about before written consent is obtained. The Screening Visit should occur 30 to 60 days prior to the Application Visit.

The Application Visit will be separated into pre-ITN application and post-ITN application assessments. CDVA, slit-lamp examination, TMH measurement via OCT, and tear collection will occur at least 45-minutes prior to ITN application, and will be performed again following ITN application. Impression cytology will be performed following these procedures after ITN application.

Safety measures will be assessed before and after ITN application at the Application Visit, including CDVA and slit-lamp biomicroscopy. AEs will be queried prior to study exit.

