### 6.1. Study Interventions Administered

Study Intervention	TrueTear Intranasal Tear Neurostimulator (ITN) – Intranasal Application	TrueTear Intranasal Tear Neurostimulator (ITN) – Extranasal Application (Control)
Number and Timing of Interventions	Single application at Application Visit	Single application at Application Visit
Manufacturer	Allergan	Allergan

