## Intranasal Tear Neurostimulator

**Table 8–1** Effectiveness Assessments

Assessment	Timing	Measurement
Goblet cell degranulation	

• Screening Visit

• Application Visit after randomized ITN application

	Impression cytology followed by immunofluorescence staining

[figure not shown]
Intranasal Tear Neurostimulator

A large black rectangular box redacting the majority of the page content.

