#### **8.6.7. Adverse Events of Special Interest**

AEs related specifically to impression cytology, including:

- Conjunctival hyperemia
- Chemosis (swelling)
- Discomfort (foreign body sensation, pain)
- Allergic reaction

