### **9.4.2. Safety Analyses**

The safety analysis will be performed using the safety population. The numbers and percentage of participants reporting AEs will be tabulated regardless of causality. Frequency of device and procedure related AEs, as well as AESIs will be summarized.

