#### AE of Special Interest

An AESI (serious or nonserious) is one of scientific and medical concern specific to the sponsor's study drug/device or program, which warrants ongoing monitoring and rapid communication by the investigator to the sponsor. Such an event might warrant further investigation in order to characterize and understand it.

There are no AESIs identified for the study interventions. AESIs pertaining specifically to impression cytology are identified in Section [8.6.7](#).

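### AESI and procedure-related AE frequencies are confined to device-treated participants, although every AESI is a reaction to impression cytology, which is first done at Screening

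*Protocol*

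**What the plan says.** Section 9.3 of the protocol defines two populations. ITT is everyone randomised. For safety, "The safety population includes all treated participants who receive" one or more administrations of the study intervention, summarised by the intervention actually received. Section 6.1 makes that intervention a device use: "Single application at Application Visit".

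Section 9.4.2 then fixes the population, "The safety analysis will be performed using the safety population", and in the same paragraph promises the output: "Frequency of device and procedure related AEs, as well as AESIs will be summarized".

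The AESIs belong to a different exposure. Section 8.6.7 defines them as "AEs related specifically to impression cytology, including" conjunctival hyperemia, chemosis, discomfort and allergic reaction. Appendix 2 (section 10.2) adds: "There are no AESIs identified for the study interventions".

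Table 8-1 schedules goblet cell sampling ("Impression cytology followed by immunofluorescence staining") at the Screening Visit and again at the Application Visit after the device has been used. On the interval, section 4.1 says: "The Screening Visit should occur 30 to 60 days prior to the Application Visit".

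**The concern.** The exposure that defines every AESI is cytology, but the denominator is defined by device use. The two sets differ by those who have the first cytology and never receive the device. Randomisation takes place at Screening (4.1, 6.3, 8), so a participant can be randomised, have cytology, withdraw during the following 30 to 60 days, and be in ITT but outside the safety population.

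That exclusion may be selective, because a bad reaction to the first cytology is a plausible reason not to come back for a second. A frequency computed only in those who returned is then conditional on an event that follows the exposure and may depend on its outcome. At stake is whether the reported cytology safety rate describes the people who had cytology. The primary effectiveness result is not touched.

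**Working it through.** **Tracing the denominator**

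1. Exposure for AESIs: impression cytology only (8.6.7, Appendix 2).
2. First exposure: Screening (Table 8-1), 30 to 60 days before Day 0 (4.1).
3. Entry to the safety population: device use on Day 0 (9.3, 6.1).
4. Population for AESI and procedure-related frequencies: the safety population (9.4.2). No other denominator is given.
5. A randomised participant with Screening cytology and no device use is therefore in no reported frequency.

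For participants who are later treated, Screening reactions can still be counted. Section 9.4.2 does not limit AESIs to treatment-emergent events; only the TEAE and TEADE tables of 9.4.2.1 carry that restriction.

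**How many could be excluded**

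The plan's figures in 9.2 are 24 + 12 = 36 treated and about 50 enrolled. Let k be the number with Screening cytology and no device use.

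- Upper bound: k = 50 − 36 = 14, or 14/50 = 28% of Screening cytologies.
- Lower bound: k = 0. Sections 4.1, 5 and 10.5 give 36 participants, and some of the 50 may never have cytology.
- k = 5 is an arbitrary middle value: 5/41 = 12.2%.

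**Effect on the rate**

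The protocol gives no AESI risk and no precision figure for safety rates, so the risks below are assumptions. Let p be the risk per cytology in returners and q the risk in non-returners. All 36 treated are taken to have both cytologies.

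*Screening-visit rate.* All-exposed rate minus treated-only rate = k/(36 + k) × (q − p).

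- q = p: zero for any k.
- q − p = 10 points: 0, 1.2 and 2.8 points at k = 0, 5 and 14.
- Stress case, p = 10%, q = 40%, k = 14: (36 × 10% + 14 × 40%)/50 = 18.4%, a shift of 8.4 points.

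*Participant-level rate (at least one AESI in the study).* With p = 5% and independent cytologies, the treated-only rate is 1 − 0.95² = 9.75%. The all-exposed rate is (36 × 9.75% + k × q)/(36 + k).

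| k | q | All-exposed rate | Treated-only minus all-exposed |
|---|---|---|---|
| 5 | 5% | 9.17% | +0.58 points |
| 5 | 15% | 10.39% | −0.64 points |
| 14 | 5% | 8.42% | +1.33 points |
| 14 | 15% | 11.22% | −1.47 points |

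The sign changes at q = 9.75%. Returners have two cytologies and non-returners one, so the treated-only rate can be too high as well as too low.

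*Sampling error.* The 95% half-width for a 10% rate in 36 is 1.96 × √(0.1 × 0.9/36) = 9.8 points.

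*Chance that a case is left out.* With k = 14, the chance that at least one excluded participant had an AESI is 1 − (1 − q)¹⁴: 25%, 51% and 77% at q = 2%, 5% and 10%.

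**The case against.** A device-treated safety population is conventional, the study is small, single-site, post-market and labelled exploratory (10.5), and no decision rule rests on the AESI rate. Individual cases are well protected. AEs are collected from consent (8.6.1). Events that are procedure-related or lead to discontinuation must be followed (7.2, 8.6). Appendix 2 calls for rapid communication of AESIs to the sponsor, and 9.4.2.1 plans an AE listing. A supplementary table by visit is also something a SAP could add.

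Most of this stands, and it sets the priority. It does not remove the point. The convention suits device events, which the proposal leaves alone, and a listing is not the frequency that 9.4.2 promises. The population is not left open either: 9.3 and 9.4.2 fix it, so a SAP that follows them inherits the mismatch.

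Three stronger readings are tempting and are not supported:

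- *Screening reactions are lost.* They are not, given the collection, follow-up and listing provisions above.
- *About 14 participants will be missing.* The order of the Screening procedures is redacted, and enrolled may include people who never had cytology. The gap between 36 and 50 is not evidence of withdrawal after cytology.
- *Non-serious reactions in screen failures are discarded because 5.4 names only SAEs.* Section 5.4 sets a minimum and is compatible with 8.6.1. Randomised non-returners have entered the study under section 8, so they are not screen failures.

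**Conclusion.** The point holds as a mismatch between exposure and denominator in a stated analysis rule. AESI and procedure-related frequencies are reported only in device-treated participants, and those who had Screening cytology but did not reach Day 0 are outside them.

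The size is unknown and probably small. Between 0 and at most 14 participants are affected. With the moderate assumed risks, shifts run from 0 to 2.8 points. It takes the maximum k together with an assumed 30-point risk gap to reach 8.4 points, still below the 9.8-point half-width. A reader might infer that the AESI rate is understated. The documents do not fix that direction: the Screening rate is understated only if non-returners have the higher risk, and the participant-level rate can err either way. The structural conclusion needs no assumption about risk; every percentage-point figure does. Priority is minor.

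**What to change.** In 9.3, add a set for procedure safety: all participants who had impression cytology at the visit in question. In 9.4.2, summarise AESIs and cytology-related AEs in that set by visit, with one summary for Screening and one for Day 0 by application group. Keep the device-treated safety population for device-related AEs and for the TEAE/TEADE tables.

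The Day 0 rows would barely change, because cytology there follows device use. The gain is in the Screening row. The layout also avoids showing a reaction to a cytology done 30 to 60 days before any device use under a device arm, which the as-received rule in 9.3 would otherwise imply.

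The cost is one extra table whose denominator differs from that of the treatment-emergent tables, with a footnote saying so. No new visit, procedure or data collection is needed, since 8.6.1 already covers events from consent. If nobody leaves between Screening cytology and Day 0, the set of participants is the same and the new denominator changes nothing.

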#### **9.4.1. Effectiveness Analyses**

The effectiveness analyses will be based on the ITT population. The ITT population is considered as the primary analysis population.

##### **9.4.1.1. Primary Effectiveness Endpoint**

- The mean change in goblet cell degranulation post-intranasal application of the ITN at the Application Visit compared to without-intranasal application of the ITN at the Screening Visit.

Intranasal Tear Neurostimulator

#### **9.4.1.3. Primary Effectiveness Analyses**

The primary effectiveness variable will be the number of goblet cells degranulated in the study eye. The study eye will be the eye with the lower tear meniscus height prior to the application or, if both eyes are equal, the right eye.

The primary effectiveness endpoint will be the mean change in goblet cell degranulation post-intranasal application of the ITN at the Application Visit compared to without-intranasal application of the ITN at the Screening Visit. Summary statistics of count, mean, median, minimum, and maximum will be provided to evaluate the change in the number of degranulated goblet cells and a 95% CI will also be provided.

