### 3. Objectives and Endpoints

Objectives	Endpoints

Primary:
 
To evaluate the change in goblet cell degranulation following randomized application of device
 

• Immunofluorescence staining of cells obtained via impression cytology

 
[REDACTED]
	

• Mean change in goblet cell degranulation post-intranasal application of the ITN at the Application Visit compared to without-intranasal application of the ITN at the Screening Visit.

[REDACTED]

Intranasal Tear Neurostimulator

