#### 4.1.1. Clinical Hypotheses

Post-application of the ITN, a greater percentage of goblet cells will be degranulated relative to pre-application of the ITN as measured by immunofluorescence staining of cells collected by impression cytology.

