# 9. Statistical Considerations

## 9.1. Statistical Hypotheses

For the primary effectiveness analysis of mean change in goblet cell degranulation post-intranasal application of the ITN compared to without-intranasal application of the ITN, the null and alternative hypotheses are as follows:

- Null hypothesis: Intranasal application of the ITN is equally effective in improving mucin secretion, as measured by the mean change in goblet cell degranulation, post-ITN application at the Application Visit versus without-ITN application at the Screening Visit.
- Alternative hypothesis: Intranasal application of the ITN is not equally effective in improving mucin secretion, as measured by the mean change in goblet cell degranulation, post-ITN application at the Application Visit versus without-ITN application at the Screening Visit.

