## 9.2. Sample Size Determination

Approximately 36 participants are required to apply randomized device and complete the Application Visit, in which 24 participants will be in the intranasal ITN application group and 12 will be in the extranasal ITN application group. Approximately 50 participants may be enrolled to meet this goal.

It is assumed that the standard deviation of the change in goblet cell degranulation post-ITN application versus pre-ITN application is 4.52. With 24 participants in the intranasal ITN application group, it is estimated that the accuracy of a half width of the 95% CI is approximately 1.8.

Intranasal Tear Neurostimulator

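### The clinical hypothesis concerns the percentage of goblet cells degranulated, the primary variable and its 95% CI are the number degranulated, and the planned precision carries no unit

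*Protocol*

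**What the plan says.** Section 4.1.1 (Clinical Hypotheses) predicts that "a greater percentage of goblet cells will be degranulated relative to pre-application of the ITN". The assay it names ("as measured by immunofluorescence staining of cells collected by impression cytology") is the one given under the primary objective in section 3: "Immunofluorescence staining of cells obtained via impression cytology".

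Section 2.1 (Study Rationale) says the trial builds on pilot study OCUN-003. It reports that pilot's result as a higher ratio of degranulated to non-degranulated cells after stimulation.

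Section 9.4.1.3 (Primary Effectiveness Analyses) defines the variable differently: "The primary effectiveness variable will be the number of goblet cells degranulated in the study eye". It uses the same scale again for the summary statistics and the 95% CI, which are there "to evaluate the change in the number of degranulated goblet cells".

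The remaining statements on the primary endpoint name no scale. Section 9.4.1.1 has "The mean change in goblet cell degranulation post-intranasal application of the ITN at the Application Visit", and section 9.1 has "as measured by the mean change in goblet cell degranulation, post-ITN application at the Application Visit versus without-ITN application at the Screening Visit". Section 9.2 assumes that "the standard deviation of the change in goblet cell degranulation post-ITN application versus pre-ITN application is 4.52" and derives a 95% CI half-width of about 1.8 for 24 intranasal participants. It gives no unit for either figure.

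**The concern.** A percentage and a ratio of degranulated to non-degranulated cells both describe the state of whichever goblet cells were collected. A number of degranulated cells depends on that state and also on how many goblet cells the impression picked up. Each participant contributes two separate impressions, one at Screening and one after application, and nothing visible says that the total scored is held equal.

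Followed as written, the primary interval therefore answers a different question from the one in section 4.1.1, and no other hypothesis names a scale that would connect them. The results could appear to contradict the hypothesis, or to support it, because cell yield changed between visits.

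The missing unit adds to this. Section 9.2 justifies the sample size only by the width of the interval. A reader who cannot tell what 1.8 measures cannot judge whether that precision is adequate for the hypothesis.

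**Working it through.** **1. The stated precision.** Inputs from section 9.2: SD of the change 4.52, n = 24 (intranasal group), 95% confidence. With the normal quantile:

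half-width = 1.96 × SD / √n = 1.96 × 4.52 / √24 = 1.81

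This agrees with the stated value of about 1.8. The half-width takes whatever unit the SD has, so the agreement does not show whether cells or percentage points were planned.

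**2. The scale in each section.**

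| Protocol section | Scale |
|---|---|
| 2.1 Study Rationale (pilot result) | ratio, degranulated to non-degranulated |
| 4.1.1 Clinical Hypotheses | percentage |
| 3 and 9.4.1.1 (endpoint) | none named |
| 9.1 Statistical Hypotheses | none named |
| 9.2 Sample Size Determination | none; 4.52 and 1.8 without unit |
| 9.4.1.3 (variable, summary, 95% CI) | number |

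The two places outside the analysis section that name a scale use a relative one. The analysis section uses an absolute one.

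**3. When the scales agree.** Let N1 and N2 be the goblet cells scored at the two visits, and p1 and p2 the proportions degranulated. The number degranulated is N × p, so its change splits into two parts:

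N2·p2 − N1·p1 = N2·(p2 − p1) + p1·(N2 − N1)

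The first part follows the percentage. The second is cell yield alone and vanishes only if N1 = N2. If the same N is scored in every sample, the number is simply N times the proportion and the two scales carry the same information.

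**4. Illustration.** All counts here are assumed; none comes from the protocol.

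| Screening | After application | Change in number | Change in percentage | Ratio, degranulated to not |
|---|---|---|---|---|
| 40 of 100 (40%) | 50 of 100 (50%) | +10 | +10 points | 40/60 = 0.67 → 50/50 = 1.00 |
| 40 of 100 (40%) | 30 of 60 (50%) | −10 | +10 points | 40/60 = 0.67 → 30/30 = 1.00 |
| 20 of 50 (40%) | 30 of 100 (30%) | +10 | −10 points | 20/30 = 0.67 → 30/70 = 0.43 |

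The formula for the second row gives 60 × 0.10 + 0.40 × (60 − 100) = 6 − 16 = −10. For the third row it gives 100 × (−0.10) + 0.40 × (100 − 50) = −10 + 20 = +10.

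In the first row, where the total is fixed, all three measures agree. In the other two, the ratio used for the pilot moves with the percentage and against the number. These rows show that a change of sign is possible, not that it is likely here.

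**The case against.** **The analysis section is clear.** It says number twice, and an analyst would know what to compute. That stands, but it settles only what will be computed. It does not make the result an answer to section 4.1.1.

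**The practical consequence depends on text that is blacked out.** The cytology detail in section 8.3 may contain a fixed-count scoring rule, and other endpoint text is also not visible. This stands and limits the point. Under such a rule the two scales would be equivalent, and only the wording and the unit would need attention. The two visible statements would still differ.

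**Leave it to the SAP.** The protocol has itself fixed the primary variable, and section 9.4.1.4 defers detail to the SAP only for the exploratory endpoints. An SAP that chose the percentage would contradict section 9.4.1.3; one that chose the number would leave section 4.1.1 unanswered.

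**Either scale would remove the contradiction.** As a matter of wording this is correct. The percentage is preferable only where the number scored is not fixed, because a number then carries cell yield as well.

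**The interval of 30 to 60 days between the impressions affects both scales.** This also stands. Only a difference in cell yield separates the number from the percentage, so the interval is not part of the case.

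**Stronger readings that a reader might infer.** One is that 4.52 is in cells, so that the planned precision fails for the percentage. The documents do not support this: section 9.2 uses the same unscaled term as the endpoint, and the pilot result was a ratio. For the same reason 1.8 cannot be converted into percentage points. Another is that the count is known to mislead in this trial. Without the scoring rule, that cannot be said.

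**Conclusion.** The point holds as an internal contradiction on the scale of the primary variable, together with a missing unit for the planned precision. Both can be read directly from the current text and rest on no assumption.

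The size of the practical effect cannot be determined. It is nil if a fixed number of goblet cells is scored in every sample. Otherwise it depends on how much cell yield differs between a participant's two impressions, and it can extend to opposite signs. The half-width of about 1.8 is arithmetically correct and is not disputed; only what it measures is unknown.

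This should be settled before the cytology data are read, because the study is open-label and the protocol text can be cited in support of either scale.

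**What to change.** Use one scale in sections 4.1.1, 9.2 and 9.4.1.3.

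- **If the number of goblet cells scored is not fixed:** make the primary variable in 9.4.1.3 the percentage degranulated, that is, degranulated cells divided by all goblet cells counted in the study-eye sample. This matches section 4.1.1 and the relative measure reported for the pilot. Keep the number degranulated as a supportive summary.
- **If a fixed number is scored in every sample:** say so, and align the wording of 4.1.1 and 9.4.1.3.
- **In either case:** state in 9.2 the unit of 4.52 and 1.8, and restate both if they are not on the chosen scale.

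The cost is a few text edits, with no additional visits or samples. If the percentage is chosen, the non-degranulated goblet cells on the same slides must also be counted. Percentages based on few cells are noisier, and the precision given in 9.2 may change. Restating it may need data that the protocol does not show.

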### 2.1. Study Rationale

The ITN delivers small electrical currents to the nasal cavity, stimulating the anterior ethmoidal branch of the trigeminal nerve, leading to activation of the nasolacrimal reflex pathway responsible for basal and bolus tear production. Numerous studies have been conducted to demonstrate that tear production is significantly increased during application of the ITN.

Tears are a complex aqueous fluid composed of proteins, lipids, and mucins. As the chemical composition of tears is essential for their optimized function, it was of interest to determine whether or not tears produced during application of the ITN were diluted (ie, reflex tears). Studies conducted to date have demonstrated equivalent lipid and protein concentrations in tears collected immediately following application of the ITN compared to baseline. In addition, mucin secretion stimulated by application of the ITN was suggested in a pilot study (OCUN-003). Specifically, a significantly higher ratio of degranulated to non-degranulated conjunctival goblet cells post-ITN stimulation was found, suggestive of mucin release.

This study aims to build on the data collected in the pilot study (OCUN-003) to verify that mucin secretion from goblet cells is stimulated with application of the ITN. These data would further support the conclusion that the tears stimulated with application of the ITN are representative of a complete basal tear as opposed to a diluted reflex fluid.

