### 2.2.2. Extranasal Control Description

The comparator arm in this study is an identical, active ITN device which will be applied extranasally as shown in [Figure 2-3](#). Participants will be instructed to place the tips of the device on the tip of the nose, hydrogel side down.

**Figure 2-3** Schematic Showing Location of Tips for Extranasal Control Application

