### **6.3. Measures to Minimize Bias: Randomization and Blinding**

At the time of randomization at the Screening Visit, qualified participants will be randomly assigned in a 2:1 ratio to receive either intranasal ITN or extranasal (control) ITN stimulation at the Application Visit. Electronic randomization methods will be used to create a randomization scheme prior to study start.

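### The stated primary estimate is the intranasal arm's change over 30 to 60 days and does not use the randomised extranasal comparator, so on its own it cannot separate an effect of stimulation from changes shared by both arms

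*Protocol*

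**What the plan says.** The protocol describes the primary quantity in the same way throughout:

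- Section 9.4.1.3 gives the endpoint as the "mean change in goblet cell degranulation post-intranasal application of the ITN at the Application Visit compared to without-intranasal application", with Screening as the reference visit. Sections 3 and 9.4.1.1 repeat it.
- The hypotheses in 9.1 compare "post-ITN application at the Application Visit versus without-ITN application at the Screening Visit". No between-arm term appears.
- The precision statement in 9.2 rests on one arm: "With 24 participants in the intranasal ITN application group, it is estimated that the accuracy of a half width of the 95% CI" is about 1.8, from an assumed SD of change of 4.52.
- Section 4.1.1 states the clinical hypothesis as a pre/post comparison.

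The design around this quantity is a randomised, controlled one:

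- Section 6.3: "qualified participants will be randomly assigned in a 2:1 ratio to receive either intranasal ITN or extranasal (control) ITN stimulation".
- Section 2.2.2: "The comparator arm in this study is an identical, active ITN device which will be applied extranasally".
- Section 3 words the primary objective as "To evaluate the change in goblet cell degranulation following randomized application of device".

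The two visits are 30 to 60 days apart (4.1). Table 8-1 schedules impression cytology at Screening and after the randomised application, and lists no sample on Day 0 before application.

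**The concern.** The aim is causal. Section 2.1 wants "to verify that mucin secretion from goblet cells is stimulated with application of the ITN", and 4.2 speaks of confirming the device's effect on mucin release. A single-arm change between two visits a month or two apart contains the stimulation effect plus anything else that moved between the visits: the course of the disease, visit conditions, or a second impression cytology. Randomisation removes shared changes of this kind only if the arms are compared, and the stated primary does not compare them.

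Section 4.2 reports that the pilot found both a pre/post change and an intranasal-versus-extranasal difference. This trial collects data for both, but its stated primary uses only the one that is confounded with time. The risk is that an interval excluding zero is read as proof of the mechanism when it cannot carry that conclusion alone.

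**Working it through.** **Inputs.** From 9.2: SD of change 4.52 (unit not stated), 24 intranasal and 12 extranasal completers, 95% CI. Assumed: the same SD in the extranasal arm and, for ANCOVA, equal variances at both visits and in both arms with a Screening/Day-0 correlation ρ of 0.3 to 0.7. The protocol gives neither the control SD nor ρ.

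**1. Reproduce the plan's figure.** SE = 4.52/√24 = 0.923.
- Normal quantile: 1.96 × 0.923 = 1.81, the stated 1.8.
- t with 23 df: 2.069 × 0.923 = 1.91.
- Alternatives do not match. All 36 pooled gives 1.96 × 4.52/√36 = 1.48, and the arm difference gives 3.13 (step 4).

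So the 12 extranasal participants do not enter the primary precision.

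**2. What the within-arm interval can show.** If the observed SD equals 4.52, any mean change above 1.91 (1.91/4.52 = 0.42 SD) gives a t interval excluding zero, whatever produced the change. As an illustration only, suppose stimulation has no effect and both arms share a change of 1, 2 or 3. The intranasal interval would then exclude zero with probability 0.18, 0.55 or 0.88, while the arm difference would do so with probability 0.05. These sizes are assumptions, because the protocol gives no drift figure.

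**3. Extranasal change alone.** SE = 4.52/√12 = 1.305. The half-width is 2.56 (z) or 2.201 × 1.305 = 2.87 (t, 11 df). Two separate intervals this wide, shown side by side, do not settle whether the arms differ. The difference needs its own interval.

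**4. Arm difference, unadjusted.** SE = 4.52 × √(1/24 + 1/12) = 1.598. The half-width is 1.96 × 1.598 = 3.13 (z) or 2.032 × 1.598 = 3.25 (t, 34 df).

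**5. Arm difference, ANCOVA on the Screening value.** The change score has variance 2σ²(1−ρ) and the ANCOVA residual has σ²(1−ρ²), so the SE shrinks by √((1+ρ)/2). With t on 33 df = 2.035:

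| ρ (assumed) | SE | Half-width | Difference for 80% power |
|---|---|---|---|
| 0.3 | 1.288 | 2.62 | 3.72 |
| 0.5 | 1.384 | 2.82 | 3.99 |
| 0.7 | 1.473 | 3.00 | 4.25 |

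**6. Power by noncentral t, two-sided 5%.** The unadjusted difference needs 4.61 for 80% power. Its power is 23% at a difference of 2 and 45% at 3. The within-arm change needs 2.70 for 80% power.

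**7. Sensitivity to the control SD.** With intranasal SD 4.52 and control SD 3 or 6, the unadjusted Welch half-width is 2.58 or 4.13.

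**The case against.** The strongest reply is that the protocol does what it sets out to do. Section 4.1.1 poses a pre/post hypothesis, and sections 3, 9.1, 9.2, 9.4.1.1 and 9.4.1.3 follow it. Appendix 5 labels the study exploratory, 9.2 is based on precision rather than power, and no success criterion is tied to the interval. At 24 versus 12 the arm difference is imprecise. The control is itself an active device, so any extranasal effect would shrink the contrast. This stands, and it is why making the arm difference primary is a trade-off rather than a required correction. It does not remove the confounding with time, given the causal aim in 2.1 and 4.2.

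A second reply is that the extranasal change may already be covered. Effectiveness is analysed in the ITT population (9.4.1), which is summarised by randomised group (9.3). Part of the objectives table, the schedule and section 9.4.1.2 are not shown, and exploratory detail is left to the SAP. A reader might infer from the visible text that no between-arm comparison is planned. The document does not support that inference. What can be said is that any such comparison lies outside the stated primary.

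A third reply is that 6.4.3 limits some sources of drift, with stable drop dosing, no drops within 2 hours of a visit, and restrictions on medication changes. These reduce shared change but cannot be assumed to eliminate it.

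**Conclusion.** The point holds as a limit on interpretation. The stated primary estimate cannot, on its own, attribute the intranasal change to stimulation, because changes shared by both arms over 30 to 60 days remain in it and the randomised comparator is not used. That the comparator is outside the primary precision is confirmed by arithmetic: only n = 24 in a single arm gives 1.8.

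Three stronger readings are tempting and are not supported. The primary is not internally contradictory, because the sections agree with each other and with 4.1.1. No false-positive rate can be claimed, because the protocol gives no drift figure and the probabilities in step 2 are illustrations. The arm contrast would not estimate device versus no stimulation, because the control is an active device.

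The half-widths for the difference rest on SD 4.52 in both arms and, for ANCOVA, on the assumed correlations and equal variances. The matter should be fixed, because the repair is cheap and uses data already scheduled.

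**What to change.** **Section 9.4.1.3.** Keep the within-intranasal change and its 95% CI as written. Report beside it, each with a 95% CI, (a) the extranasal change and (b) the intranasal-minus-extranasal difference in Day-0 degranulation from an ANCOVA adjusted for the Screening value. State that the within-arm change alone will not be attributed to the device, and that the contrast is intranasal versus extranasal application of an active device. If the SAP or redacted text already contains this comparison, a cross-reference and the interpretive sentence are enough.

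**Section 9.2.** Beside the within-arm half-width (1.8 by z, 1.9 by t), state the expected half-width of the difference at 24 versus 12. This is about 3.1 (z) to 3.25 (t) unadjusted with SD 4.52 assumed in both arms, and about 2.6 to 3.0 with ANCOVA at an assumed correlation of 0.3 to 0.7.

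Making the arm difference the primary is optional.

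**Cost.** Wording and two more reported intervals. No participants, samples or visits are added, because Table 8-1 already schedules cytology after randomised application and so covers both arms. The downside is that the added interval is wide and likely to be inconclusive unless the effect is large: 80% power needs a difference of about 4.6 unadjusted, or 3.7 to 4.3 with ANCOVA.
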